**Methods of analysis**

The data will be statistically processed with Statistica 10.0 software. The following tests will be used to compare data with normal distribution: two-tailed Student's test and ANOVA. The Mann-Whitney test and ANOVA will be used to compare non-normally distributed data. The regression analysis will be used for quantitative efficacy data. The categorical data will be processed using the Fisher's exact test, Yates-corrected Pearson's test  $\chi^2$  and Cochran-Mantel-Haenszel test.

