3.4.2. Inclusion criteria

1. Signing of the Informed Consent Form;
2. Male sex;
3. Age of 18 to 45 years, inclusive;
4. BMI within normal limits (18.5–24.9 kg/m²);
5. Healthy patients, which is proved by their medical history, physical examination and laboratory findings:
 - No clinically significant abnormalities of circulatory, respiratory, nervous, hematopoietic, endocrine and digestive systems, liver and kidneys in the past medical history and at screening;
 - No history of cardiovascular disorders or thyroid disorders;
 - No history of hematologic disorders, including but not limited to any type of anemia, myelodysplastic syndrome, blood cancers, hemolytic syndrome, hemoglobinopathies, coagulopathies;
 - CBC results within normal limits, including:
 - Hemoglobin within 132–173 g/L;
 - Hematocrit (based on CBC results) within 39–49%;
 - Platelet count within 150–400*10⁹/L;
 - Absolute reticulocyte count within 30.4–93.5 * 10⁹/L;
 - Blood biochemistry and urinalysis results within normal limits;
 - Serum ferritin within 20–250 µg/L;
 - Serum endogenous erythropoietin within 4.3–29.0 MIU/mL;
 - Hemodynamic parameters within normal limits: systolic blood pressure within 100–139 mmHg; diastolic blood pressure within 60–90 mmHg; heart rate within 50–90 bpm;
 - No history of chronic infections (tuberculosis) or chronic inflammation;
 - No hepatitis B or C, HIV, or syphilis;
 - No acute infections within 4 weeks prior to inclusion in the study;
 - No psychiatric disorders and other conditions (including depression) that can interfere with the volunteer's ability to follow the study protocol;

- Well-being (in the volunteer's opinion) within 30 days prior to inclusion in the study;
- 6. No history of or current (at baseline) alcohol or drug abuse;
- 7. Ability of the volunteer, in the investigator's opinion, to follow the study protocol procedures;
- 8. Willingness of volunteers and their sexual partners with preserved reproductive potential to use reliable contraception within 2 weeks before inclusion in the study and up to 7 weeks after the injection of the test product. This criterion is not applicable to subjects who underwent surgical sterilization. Reliable methods of contraception include one barrier method in combination with one of the following methods: spermicides, intrauterine device/oral contraceptives (for sexual partners).

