4.2. Pharmacodynamics Endpoints

Primary endpoint

- AUEC0-1176 h (total area under the effect vs. time curve from the moment of injection to 1176 h [Day 50 of follow-up]) based on the change in the absolute reticulocyte count after a single-dose injection of the drug product.
- AC-Emax (absolute maximum increase in the test parameter vs. baseline) based on the change in the absolute reticulocyte count in the blood after a single-dose injection of the drug product.

Secondary endpoints:

- AUEC0-1176 h (total area under the effect vs. time curve from the moment of injection to 1176 h [Day 50 of follow-up]) based on the change in the Hb level in the blood after a single-dose injection of the drug product.
- AC-Emax (absolute maximum increase in the test parameter vs. baseline) based on the change in the Hb level in the blood after a single-dose injection of the drug product.

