8.2. Description of the Statistical Methods to be Employed

Quantitative Data

The following quantitative data will be analyzed in the study:

Pharmacokinetics:

- Plasma concentration of drug,
- Area under plasma concentration curve,
- Time (e.g., maximum plasma concentration time, half-life)

- Elimination parameters (e.g. clearance, terminal rate constant)

Pain Assessment:

- VAS score

Safety:

- CBC results,
- Blood chemistry results,
- Vital signs;
- ECG findings,
- Urea analysis results,
- Skin disorders size at the sites of venipuncture,
- Skin disorders lifetime at the sites of venipuncture.

Pharmacodynamics:

- absolute reticulocyte count.
- Hb level.
- Area under effect curve «absolute reticulocyte count — time».
- Area under effect curve «Hb level — time».
- Time (e.g. the time of the maximum increase of absolute reticulocyte count vs. baseline).

The statistical analysis will include two-tailed hypothesis testing; the chosen significance level is 0.05.

Quantitative variables will be tested for normality using the Shapiro-Wilk test.

Normally distributed quantitative variables will be tested using the two-sample Student's t-test, Welch's t-test, and ANOVA.

Non-normally distributed quantitative variables will be tested using the Mann-Whitney U-test, the Wilcoxon test, the Kruskal-Wallis test, and the Friedman test.

Normally distributed quantitative data will be described using the following descriptive statistics: mean, SD, CV, min, and max. Non-normally distributed quantitative data will be described using the following descriptive statistics: median, quartiles, CV, min, and max.

Categorical Data

The following categorical data will be analyzed in the study:

Safety:

- Skin disorders sort at the sites of venipuncture.
- Rate and severity grades of AEs/SAEs,
- Rate of Grade 3-4 AEs,
- Frequency of local reactions (total and by skin disorder type).
- Frequency of early study termination cases by AEs/SAEs.

Categorical data will be processed using frequency tables, contingency tables, the Fisher's exact test, the test of equal frequencies, Pearson's χ^2 test, and the Cochran-Mantel-Haenszel test. Percentages or proportions will be used to describe categorical data.

The Benjamini-Yekutieli correction for multiple testing will be used.

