8.6. Subgroup analysis, interaction and related variables

Not available.

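### The between-group comparison of AC-Emax (reticulocytes) names no baseline covariate; a pooled baseline-adjusted model is a cheap improvement whose precision gain depends on quantities that the documents do not give

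*SAP*

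**What the plan says.** SAP 4.2 makes this a primary PD endpoint: "AC-Emax (absolute maximum increase in the test parameter vs. baseline) based on the change in the absolute reticulocyte count in the blood". It is a change score, the volunteer's peak minus the pre-dose value. Time 0 is in the PD time set of SAP 8.4, so the pre-dose value is available for every volunteer.

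SAP 8.2 gives the tests. For normal data: "Normally distributed quantitative variables will be tested using the two-sample Student's t-test, Welch's t-test, and ANOVA". Otherwise: "Non-normally distributed quantitative variables will be tested using the Mann-Whitney U-test, the Wilcoxon test, the Kruskal-Wallis test, and the Friedman test". On the error rate it says: "The statistical analysis will include two-tailed hypothesis testing; the chosen significance level is 0.05". None of these entries carries a covariate. The section where one would be named, "8.6. Subgroup analysis, interaction and related variables", reads in full "Not available". SAP 9 plans no further analyses.

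Two passages leave some room. The Protocol (Methods of analysis) states: "The regression analysis will be used for quantitative efficacy data". It names neither an endpoint nor a baseline term. The close of SAP 8.2 allows methods to be chosen, and the list to grow, once the data are in.

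SAP 3.1 describes the BCD-131 part of stage I as open-label and non-randomized. Cohorts of 3 enter one after another and grow to 6 only after a DLT. Mircera and Aranesp have 6 volunteers each. The stage II dose is chosen after stage I by comparing BCD-131 with these two products.

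**The concern.** Subtracting baseline is not the same as adjusting for it. Unless a volunteer's peak rises one for one with his baseline, the increase still depends on where he started. Eligible baselines span about threefold ("Absolute reticulocyte count within 30.4–93.5" × 10⁹/L), and a mean of 3 volunteers against a mean of 6 can differ noticeably at baseline. Because BCD-131 cohorts are filled in sequence and not randomized against the comparators, such a difference need not be pure chance.

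AC-Emax is one of the two primary PD measures available when a BCD-131 dose with PD effects similar to the comparators is sought. A residue of baseline imbalance could make a dose look nearer to, or further from, a comparator than it is. The data needed to remove that residue are already collected.

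**Working it through.** **The plan's own counts.** The seven listed cohorts × 6 + 12 comparator volunteers = 54 at stage I, and 54 + 12 = 66 in total. Both match the documents. The minimum stage I size with all cohorts opened is 7 × 3 + 12 = 33 in nine groups, so 33 − 9 = 24 error df, or 23 with a covariate. The documents give no SD, correlation, slope or power for any PD comparison. Those below are assumptions.

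**Step 1: size of a chance baseline imbalance, 3 v 6.** SE = SD × √(1/3 + 1/6) = 0.707 × SD. The entry range is 93.5 − 30.4 = 63.1.

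| Assumed baseline SD (× 10⁹/L) | SE of difference | 95% span |
|---|---|---|
| 63.1/6 = 10.5 | 7.4 | ±14.6 |
| 63.1/4 = 15.8 | 11.2 | ±21.9 |
| 63.1/√12 = 18.2 (uniform) | 12.9 | ±25.2 |

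**Step 2: how much stays in AC-Emax.** If peak = a + b × baseline + error, the change score has slope b − 1 on baseline, so an imbalance d leaves (b − 1)d. For baseline SD 15.8 the 95% span left is:
- b = 0.3: ±15.3
- b = 0.5: ±10.9
- b = 0.7: ±6.6
- b = 0.9: ±2.2
- b = 1: none
- b = 1.2: ±4.4, with the sign reversed.

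**Step 3: precision, equal SDs at baseline and peak (so b = ρ).** In units of that SD squared, the change-score variance is 2(1 − ρ). The ANCOVA variance is (1 − ρ²) times a penalty for estimating the slope, 1 + 1/(ν − 2), with ν the within-group df. For the pooled model ν = 24 and the penalty is 1 + 1/22. Power is from the noncentral t at a true difference of 1.5 SD, with noncentrality 1.5/√(variance × 0.5), two-sided 0.05.

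| ρ | Change score | Pooled ANCOVA | Ratio | Power, unadjusted (24 df) to adjusted (23 df) |
|---|---|---|---|---|
| 0.3 | 1.40 | 0.91 × 1.045 = 0.95 | 0.68 | 41% to 55% |
| 0.5 | 1.00 | 0.75 × 1.045 = 0.78 | 0.78 | 53% to 63% |
| 0.7 | 0.60 | 0.51 × 1.045 = 0.53 | 0.89 | 75% to 79% |

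At ρ = 0.9 the ratio is 0.99, so there is practically no gain. The power figures omit the Benjamini-Yekutieli correction of SAP 8.2 and need all seven cohorts to be opened.

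**Step 4: unequal SDs.** Let k = peak SD / baseline SD, so b = kρ. The variance ratio is k²(1 − ρ²)/(1 + k² − 2ρk), times 1 + 1/22.

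| k | ρ = 0.3 | ρ = 0.5 | ρ = 0.7 |
|---|---|---|---|
| 1.5 | 0.91 | 1.01 | 1.04 |
| 2 | 1.00 | 1.05 | 0.97 |

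At k = 2 and ρ = 0.5 the slope is exactly 1. There is then nothing to remove, and only the 1/22 (about 5%) penalty is paid.

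**Step 5: why pooled and not pairwise.** On 9 volunteers ν = 7 and the penalty is 1 + 1/5 = 1.2. With equal SDs the variance ratio is 0.78, 0.90, 1.02 and 1.14 at ρ = 0.3, 0.5, 0.7 and 0.9. After the change from 7 to 6 df, the interval is narrower only for ρ below about 0.55.

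**Step 6: validity of the unadjusted test.** In simulation (3 v 6, normal data, random allocation, 20,000 runs per setting) the type I error of the unadjusted change-score t-test was 0.048 to 0.051 for ρ from 0.3 to 0.9.

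**The case against.** The strongest case against acting has four parts.

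1. **No error is shown.** Under random allocation the unadjusted test holds its level, so this is an efficiency preference in a phase 1 study with no power target. That stands for chance imbalance. It does not cover BCD-131 cohorts enrolled in sequence without randomization, because the simulation assumes random allocation.
2. **The gain depends on the SD ratio.** A peak taken over 14 post-dose times after a drug meant to raise the count may well vary more than baseline. Step 4 then shows little gain or a small loss. This stands, and it limits the claim.
3. **The model has its own assumptions.** It needs a common slope and common variance over doses from 0.05 to 4.45 µg/kg (89-fold) and two other products, and 3 per cohort cannot check these well. This also stands. It is a reason to keep the unadjusted summaries in view.
4. **The documents are not closed to adjustment.** The Protocol mentions regression, SAP 10 declares no deviation from the Protocol's methods, and SAP 8.2 lets the list grow. This mitigates only in part, because none of these passages names baseline. A covariate added after the data are seen in an open-label study is not prespecified.

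A reader might infer that the whole imbalance passes into the comparison, or that adjustment narrows every estimate. Steps 2, 4 and 5 contradict both. It would also go too far to say that a volunteer who starts low must show a larger increase, since this reverses when the slope exceeds 1.

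**Conclusion.** The point holds as a cheap improvement and not as an error in the plan. No baseline term is prespecified for a primary PD endpoint whose baseline is collected, and a share (b − 1) of any baseline imbalance stays in the comparison.

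The precision gain is conditional: variance falls by about 32%, 22% or 11% at ρ = 0.3, 0.5 or 0.7 if the two SDs are equal, and changes little (ratio 0.91 to 1.05) if the peak SD is 1.5 to 2 times the baseline SD. The firmer benefit is that the residual imbalance is removed whatever the slope, provided that the relation is linear with a common slope. The model adjusts for the baseline count only, not for other differences between cohorts enrolled at different times.

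A reader might infer that the stage II dose will be chosen by one of the tests in SAP 8.2. The documents do not say so. SAP 3.1 describes a comparison that seeks similar PD effects and names no test, contrast or similarity limit. That is a separate and larger gap. Power to detect a difference, as in Step 3, is therefore a gauge of precision and not the operating characteristic of the dose choice.

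**What to change.** In SAP 8.2 and 8.6, prespecify for AC-Emax (reticulocytes as primary, Hb as secondary) one linear model over all stage I groups, with group as factor and the pre-dose value of the same marker as covariate, common slope. Do not fit separate pairwise ANCOVAs on 9 volunteers. Report the adjusted difference of each BCD-131 dose from Mircera and from Aranesp with 95% CIs. Use the analogous model for IV v SC in stage II. Keep the unadjusted summaries beside the adjusted ones.

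The cost is SAP wording, with no added volunteers or samples. One error df is lost (24 to 23 in stage I at the minimum size, 10 to 9 in stage II). If the slope is near 1, variance rises by up to about 5% in stage I. By the same formula the stage II penalty is 1 + 1/(10 − 2) = 1.125, so the loss there could reach about 12.5%. The common-slope and common-variance assumptions should be stated as such.

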3. STUDY DESIGN

3.1 Design

Stage I

Stage I of clinical study BCD-131-1 is an open-label, non-randomized clinical study of pharmacokinetics, pharmacodynamics, tolerability, safety and immunogenicity of the novel drug product given to healthy volunteers at ascending doses (Phase 1, a traditional “3+3” design). Also, at stage I the investigators will evaluate the PK and PD parameters of the closest analogues of BCD-131 (Mircera[®] and Aranesp[®]) given as subcutaneous injections at therapeutic doses.

Volunteers (no more than 54 subjects at stage I) will be included in the study after they have signed an informed consent form, completed an examination at screening (no more than 14 days) and received the approval of the investigator confirming their eligibility for the study.

Evaluation of pharmacokinetics, pharmacodynamics and safety of ascending doses of BCD-131

The evaluation of pharmacokinetics, safety and tolerability of BCD-131 will be conducted in 8 cohorts:

1. Cohort 01 will include no more than 6 volunteers who will receive a single subcutaneous injection of BCD-131 at a dose of 0.05 µg/kg body weight.
2. Cohort 02 will include no more than 6 volunteers who will receive a single subcutaneous injection of BCD-131 at a dose of 0.15 µg/kg body weight.
3. Cohort 03 will include no more than 6 volunteers who will receive a single subcutaneous injection of BCD-131 at a dose of 0.40 µg/kg body weight.
4. Cohort 04 will include no more than 6 volunteers who will receive a single subcutaneous injection of BCD-131 at a dose of 1.05 µg/kg body weight.
5. Cohort 05 will include no more than 6 volunteers who will receive a single subcutaneous injection of BCD-131 at a dose of 1.70 µg/kg body weight.
6. Cohort 06 will include no more than 6 volunteers who will receive a single subcutaneous injection of BCD-131 at a dose of 2.75 µg/kg body weight.
7. Cohort 07 will include no more than 6 volunteers who will receive a single subcutaneous injection of BCD-131 at a dose of 4.45 µg/kg body weight.

Volunteers will be included in the study in a consecutive order. First, three volunteers will be included in Cohort 01 to receive a single subcutaneous injection of BCD-131 at a calculated starting safe dose of 0.05 µg/kg. If during 14 days after the injection these volunteers do not develop any treatment-emergent Grade 3–4 adverse events, the next three volunteers will be included in the study (Cohort 02). The further inclusion algorithm is as follows:

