3.4. Selection of Study Population

3.4.1. Planned Sample Size

Up to 66 healthy volunteers.

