6. SAMPLE SIZE CALCULATION

The sample size for the study was calculated based on the “3+3” design used in the study of doses and additional test parameters:

Cohort	Dose, µg/kg	Number of volunteers to be enrolled (obligatory)	Number of volunteers who can be enrolled if DLT signs develop
01	0.05	3	3
02	0.15	3	3
03	0.40	3	3
04	1.05	3	3
05	1.70	3	3
06	2.75	3	3
07	4.45	3	3

To assess the PK and PD of the closest analogues of BCD-131, 6 more volunteers will be included in the study to receive Mircera® and 6 more volunteers will be enrolled to receive Aranesp®.

To assess the PK and PD of BCD-131 given as a subcutaneous or intravenous injection at a dose established at stage I of the study, 6 more volunteers will be included in the study to receive BCD-131 as an intravenous injection and 6 more volunteers will be enrolled to receive BCD-131 as a subcutaneous injection.

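### No log-scale analysis or geometric summary is prespecified for AUC and Cmax across an 89-fold dose range; a raw-scale pooled-error ANOVA would distort contrasts in both directions if scatter is proportional to the mean

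*SAP*

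**What the plan says.** SAP 8.2 applies Shapiro-Wilk to each quantitative variable and then splits. On the normal branch, "Normally distributed quantitative variables will be tested using the two-sample Student's t-test, Welch's t-test, and ANOVA", and "Normally distributed quantitative data will be described using the following descriptive statistics: mean, SD, CV, min, and max". On the other branch the tests are rank-based and the summary is median and quartiles with CV and range. Tests are two-sided at 0.05, with a Benjamini-Yekutieli correction.

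SAP 8.4, the data conversion section, gives formulas for AUC, AUC to infinity, half-life and clearance. The only logarithmic step in the analysis of concentrations is the terminal-slope regression for the elimination constant. The protocol's Methods of analysis paragraph has no log step either.

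The closing paragraph of SAP 8.2 defers the choice of tests until the data are in and lets the list of methods grow.

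Dosing starts "at a calculated starting safe dose of 0.05 µg/kg" and the top step is "Cohort 07 will include no more than 6 volunteers who will receive a single subcutaneous injection of BCD-131 at a dose of 4.45 µg/kg". AUC is the primary PK endpoint (SAP 4.1). SAP 3.1 uses PK, PD and safety comparisons with Mircera and Aranesp to arrive at the stage II dose.

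**The concern.** AUC and Cmax are positive and can be expected to rise with dose. If between-subject scatter rises with them, the cohort SDs may differ by as much as the doses do. A raw-scale ANOVA replaces those SDs with one pooled value set mainly by the highest doses. That value is far too large for contrasts among the low doses, which then lose power. It is too small at the top dose, where false positives follow.

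At stake are the dose contrasts and the comparisons with Mircera and Aranesp on a primary PK endpoint, and the way exposure is summarised for later work. Arithmetic means and SDs also give no direct ratio between groups, which is the natural quantity for comparing exposure.

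**Working it through.** **Inputs from the documents.** Seven listed doses: 0.05, 0.15, 0.40, 1.05, 1.70, 2.75 and 4.45 µg/kg. Each cohort has 3 obligatory subjects, with 3 more under "Number of volunteers who can be enrolled if DLT signs develop". For the comparators, "6 more volunteers will be included in the study to receive Mircera® and 6 more volunteers will be enrolled to receive Aranesp". Alpha is 0.05, two-sided.

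**The plan's own figures.** 7 × 6 + 12 = 54, which matches "no more than 54 subjects at stage I". Adding 12 for stage II gives 66, which matches "Up to 66 healthy volunteers". (SAP 3.1 announces eight cohorts but lists seven; eight would give 8 × 6 + 12 = 60.) No power, SD or CV is stated, so there is nothing further to reproduce. Dose range: 4.45 / 0.05 = 89.

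**Assumptions, not in the documents.** Log-normal AUC and Cmax, proportional to dose, with a constant between-subject CV of 30%, 50% or 70%; n = 3 per dose and n = 6 per comparator; tests at an unadjusted 0.05. Simulated figures move by about one percentage point between runs.

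**Why the pooled SD misleads.** With equal n, the pooled SD is CV × root-mean-square dose. The squared doses sum to 31.54; 31.54 / 7 = 4.506, and its square root is 2.12 µg/kg.
- At CV 40% the pooled SD is 0.40 × 2.12 = 0.849. Divided by each of the four lowest doses, this is 17, 5.7, 2.1 and 0.8 times the cohort mean.
- Relative to a cohort's own SD the ratio is 2.12 / dose, whatever the CV: 42 at 0.05, 2.0 at 1.05 and 0.48 at 4.45. The error term is too large at low doses and about half what it should be at the top.

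**Pooled-error contrasts between adjacent doses, power:**

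| Contrast (µg/kg) | Raw, CV 30% / 50% / 70% | Log, CV 30% / 50% / 70% |
|---|---|---|
| 0.05 v 0.15 | 0 / 0 / 0% | 99 / 76 / 51% |
| 0.40 v 1.05 | 17 / 5.5 / 3% | 96 / 65 / 41% |
| 2.75 v 4.45 | 77 / 51 / 40% | 46 / 20 / 14% |

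The apparent raw advantage in the last row comes from the understated error term.

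**Type I error, dose cohort v a comparator with the same mean (pooled error, CV 30–70%):** at 0.05 µg/kg, raw 0%; at 1.05, raw about 1%; at 4.45, raw 19–20%. On the log scale it is about 5% at all three.

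**Pairwise t-tests, 3 v 6, CV 50%, power:**

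| BCD-131 relative to comparator | Student raw | Welch raw | Log |
|---|---|---|---|
| Half | 26% | 44% | about 44% |
| Double | 47% | 18% | about 44% |

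**Does the normality test protect?** Within a cohort of 3, Shapiro-Wilk rejects log-normal data in about 5–6% of runs, close to its nominal level; at n = 6, in 8–18%. On the 21 BCD-131 values pooled it rejects in nearly all runs. SAP 8.2 does not say which set of values is tested.

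**Does the rank branch protect?** The smallest exact two-sided Mann-Whitney p at 3 v 3 is 2 / C(6,3) = 2/20 = 0.10. At 3 v 6 it is 2 / C(9,3) = 2/84 = 0.024.

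**CL.** SAP 8.4 defines it as dose divided by AUC(0–1176). Under proportionality neither its mean nor its SD grows with dose. Simulated type I error of the ANOVA across doses is 4–5% raw and about 5% log.

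**The case against.** The plan does not commit to raw ANOVA. If Shapiro-Wilk is run on pooled values, AUC and Cmax will almost always go to rank tests, which a log transformation leaves unchanged. Welch's test allows unequal variances, and the last paragraph of SAP 8.2 permits further methods. Proportional scatter is an assumption. SAP 3.1 looks for a dose with PD effects similar to the comparators, so matching AUC or Cmax is not the stage II criterion.

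Much of this stands and limits the claim. It does not remove it. Testing within cohorts would usually select the raw branch; the rank branch has no usable pairwise test between three-subject cohorts; no rule chooses Student or Welch; and a method added after the data are seen is not prespecified. The protocol also lists ANOVA for non-normal data, so the diversion to ranks is not assured.

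A reader might infer several stronger points that the material does not support:
- *Low doses cannot be separated from anything.* At CV 40% the raw pooled contrast of 0.05 µg/kg has about 0% power against 0.15 and 0.40, but 28% against 1.05, 71% against 1.70 and 96% against 2.75.
- *Half the comparator value is always harder to detect than double.* This holds for Student's test and reverses for Welch's.
- *Raw pairwise tests always lose power.* Welch matches the log analysis for a halving, and Student slightly exceeds it for a doubling.
- *CL has the same dose-driven defect.* It is dose-normalised and does not.

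**Conclusion.** The point holds for AUC(0–1176), AUC(0–∞) and Cmax. The plan prespecifies no log-scale analysis, geometric summary or ratio, and the normal branch allows a pooled-error raw ANOVA that would give unreliable contrasts. The error is not simply a loss of power: it removes power at the lowest steps and raises the false-positive rate roughly fourfold at 4.45 µg/kg (19–20% against 5%). Raw t-tests have power that depends on the direction of the difference and on which listed test is picked; the log analysis is symmetric.

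The sizes rest on log-normal, dose-proportional exposure with a constant CV of 30–70%, none of which the documents state. They would shrink if scatter grew more slowly than the mean. They also precede the multiplicity correction. For CL, only skewness favours the log scale. This should be corrected because it touches a primary PK endpoint and one input to the dose choice. The documents do not support saying that it would lead to a wrong stage II dose, and it is not fatal to an exploratory phase 1 study.

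**What to change.** In SAP 8.2 and 8.4, prespecify that AUC(0–1176), AUC(0–∞) and Cmax are analysed after log transformation in all groups and both stages, whatever the Shapiro-Wilk result. Treat CL the same way, giving skewness as the reason. Report the geometric mean and geometric CV per group. Report geometric mean ratios of each BCD-131 dose to Mircera and to Aranesp in stage I, and of intravenous to subcutaneous BCD-131 in stage II, with confidence intervals at a stated level. Summarise Tmax by median and range.

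The cost is SAP wording only. No extra subjects, samples or visits are needed.

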2.2. Objectives

Study objectives (Stage I):

1. Establish the frequency and severity of adverse events following the administration of single ascending doses of BCD-131 to healthy volunteers.
2. Establish key pharmacokinetic (PK) parameters ($AUC_{0-1176\text{ h}}$, $AUC_{0-\infty}$, C_{\max} , T_{\max} , $T_{1/2}$, K_{el} and CL) of BCD-131 following the administration of single ascending doses of the drug product to healthy volunteers.
3. Establish pharmacodynamic (PD) parameters ($AUEC_{0-1176\text{ h}}$, $AC-E_{\max}$) of BCD-131 based on the absolute reticulocyte count and Hb values in the blood of healthy volunteers following the administration of single ascending doses of BCD-131.
4. Study serum levels of binding antibodies (BAbs) in the blood of healthy volunteers following the subcutaneous administration of single ascending doses of BCD-131.
5. Establish main PK ($AUC_{0-1176\text{ h}}$, $AUC_{0-\infty}$, C_{\max} , T_{\max} , $T_{1/2}$, K_{el} and CL) and PD parameters ($AUEC_{0-1176\text{ h}}$, $AC-E_{\max}$ based on changes in the absolute reticulocyte count and Hb levels in the blood) as well as immunogenicity of therapeutic doses of Mircera® and Aranesp® given as subcutaneous injections to healthy volunteers.
6. Establish a safe dose of subcutaneous BCD-131 to be used at stage II of the study.

Study objectives (Stage II):

CONFIDENTIAL

Version 1.0 dated 21-Sep-2015

Page 4 of 21

1. Establish key pharmacokinetic parameters ($AUC_{0-1176\text{ h}}$, $AUC_{0-\infty}$, C_{\max} , T_{\max} , $T_{1/2}$, K_{el} and CL) of BCD-131 given as a single subcutaneous or intravenous injection to healthy volunteers at a dose established at stage I of the study.
2. Establish key pharmacodynamic parameters ($AUEC_{0-1176\text{ h}}$, $AC-E_{\max}$ based on changes in the absolute reticulocyte count and Hb levels in the blood) of BCD-131 given as a single subcutaneous or intravenous injection to healthy volunteers at a dose established at stage I of the study.
3. Establish the frequency and severity of adverse events and evaluate the level of BAbs to BCD-131 given as a single subcutaneous or intravenous injection to healthy volunteers at a dose established at stage I of the study.
4. Establish subcutaneous and intravenous doses of BCD-131 to be used in a phase II clinical study.

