Statistical methods will be chosen according to the type of initial data and their distribution. Appropriate statistical tests will be established after the data collection has been completed because the type of data distribution, sample homogeneity, etc. are unknown before the study start. For appropriate data processing, the list of statistical methods used may expand during the analysis.

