8.5. Multivariate Comparison and Multiplicity

Refer to Section 8.2.

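### AE and local-reaction comparisons across the seven dose cohorts have no pre-specified dose-ordered test and fall under a Benjamini-Yekutieli correction with no defined family and no safety exemption

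*SAP*

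**What the plan says.** The first Stage I objective in SAP 2.2 is "Establish the frequency and severity of adverse events following the administration of single ascending doses of BCD-131 to healthy volunteers". SAP 6 fixes 3 obligatory volunteers at each of seven doses, with 3 more under the column "Number of volunteers who can be enrolled if DLT signs develop".

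SAP 8.2 sets the error rate: "The statistical analysis will include two-tailed hypothesis testing; the chosen significance level is 0.05". Under Categorical Data every listed item is a safety item: AE/SAE rates and grades, Grade 3-4 AEs, local reactions, withdrawals and skin findings. The methods are: "Categorical data will be processed using frequency tables, contingency tables, the Fisher's exact test, the test of equal frequencies, Pearson's χ^2 test, and the Cochran-Mantel-Haenszel". No form, strata or scores are given for the last of these. The block ends with "The Benjamini-Yekutieli correction for multiple testing will be used". Whether that sentence governs this block only or all of 8.2, safety is inside it. SAP 8.5, the multiplicity section, says only "Refer to Section 8.2". The closing paragraph of 8.2 leaves the choice of tests until the data are in and adds: "For appropriate data processing, the list of statistical methods used may expand during the analysis".

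The protocol synopsis (Methods of analysis) names similar categorical tests, with no dose-trend test and no multiplicity correction.

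**The concern.** The cohorts are ordered by dose, so the natural question about AEs is whether their frequency rises with dose. A test of any difference among seven unordered groups spreads its power over every pattern and has little left for the one that matters. A false-discovery correction mainly guards against claiming too many effects. Applied to harm, it raises the bar for real signals as well as false ones, and here nobody can say by how much because the family is not defined.

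At stake is the evidence on tolerability below the DLT threshold and outside the DLT window. SAP 3.1 bases the Stage II dose partly on a comparison of safety across BCD-131 doses and comparators, and SAP 4.4 makes total AEs and administration-site reactions endpoints.

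**Working it through.** **The plan's own figures.** Seven cohorts x 6 + 12 reference volunteers = 54 (Stage I maximum); 54 + 12 = 66 (overall maximum). Both match SAP 3.1 and 3.4.1. The text of 3.1 announces eight cohorts but lists seven doses; seven reproduces the totals and is used here. The documents give no power, AE rate or number of tests, so the AE gradients and the family size m below are assumptions, shown as ranges.

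**Inputs from the SAP.** Two-sided 0.05 (8.2); 7 cohorts of 3 = 21 volunteers (6); comparator groups of 6 and 6 (6).

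**Method.** All 4^7 = 16,384 tables of 7 cohorts x 3 volunteers were enumerated. Given t volunteers with an event in total, a table has probability ∏C(3,x_i)/C(21,t).
- Unordered exact test (Freeman-Halton): p = sum over tables no more probable than the observed one.
- Exact trend test: T = Σ s_i·x_i with scores 0 to 6 and expectation 3t; p = sum over tables with |T - 3t| at least as large as observed.
- Assumed risks: logit(p_i) = logit(0.05) + (i/6)·[logit(p_top) - logit(0.05)], i = 0 to 6.
- Benjamini-Yekutieli (BY) first-step threshold, relevant when one signal is real: 0.05/(m·Σ1/i). For m = 5: 0.05/(5 x 2.283) = 0.0044. For m = 10: 0.05/(10 x 2.929) = 0.0017.

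**Power, 3 per cohort.**

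| AE risk, lowest to highest dose | Unordered, 0.05 | Trend, 0.05 | Unordered, BY m=5 / m=10 | Trend, BY m=5 / m=10 |
|---|---|---|---|---|
| 5% to 30% | 2% | 13% | <0.2% / <0.2% | 1% / 1% |
| 5% to 40% | 4% | 22% | <0.2% / <0.2% | 3% / 2% |
| 5% to 70% | 16% | 59% | 2.2% / 1.2% | 21% / 13% |
| 5% to 85% | 29% | 81% | 5.6% / 4.1% | 42% / 29% |

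Changing one element alone recovers only part of the loss. Dropping BY but keeping the unordered test gives the second column; adding a trend test but keeping BY gives the last.

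**Sensitivity to shape and cohort size.** With risk rising linearly from 5% to 60%, the figures at 0.05 are 9% (unordered) v 38% (trend) with 3 per cohort, and 39% v 73% if every cohort had 6. The latter is an upper bound, because a cohort expands only after a DLT.

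**Pairwise and pooled comparisons (Fisher, two-sided).**
- 3/3 v 0/3: p = 2/C(6,3) = 2/20 = 0.10, so two obligatory cohorts can never differ at 0.05, with or without BY.
- 3/3 v 0/6 (one cohort against one comparator): p = 1/C(9,3) = 1/84 = 0.0119. This passes 0.05 but, as a lone signal, fails the m = 5 step of 0.0044.
- All 21 BCD-131 v all 12 comparator volunteers: unadjusted, 7/21 v 0/12 is the first to flag (p = 0.032). At m = 10 it takes 12/21 v 0/12 (p = 0.0017).

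**What zero events would exclude.** The exact 95% upper limit is 1 - 0.025^(1/n): 71% for 0/3 and 16% for 0/21.

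**The case against.** A reader might infer that dose-related harm is almost undetectable in this trial. The documents do not support that. SAP 3.1 governs escalation by counts of treatment-emergent Grade 3-4 AEs over 14 days, with no p-value and no correction. If such events rose linearly from 5% to 60%, that rule would stop escalation with probability 99.9%; from 2% to 33%, 90.5%. SAP 8.2 also gives frequency tables and percentages, which BY does not touch. This stands, and it confines the point to formal testing of events outside the rule.

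A reader might also take it that the planned tests are definitely unordered. Cochran-Mantel-Haenszel has a correlation form with ordered scores, which the SAP neither selects nor excludes, and the list of methods may grow. That stands too, but an unspecified option, or a test added after an open-label trial has been read, is not pre-specification.

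It might be inferred that a non-significant result will be read as absence of toxicity. No section says so, and the objective is one of estimation. The risk of that reading is real with such low power, but it is a risk, not a plan.

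The strongest remaining argument is that BY is not the main problem: 21 volunteers are few, and for 5% to 30% or 40% even the trend test without BY has only 13% to 22% power. This is correct. The BY figures also use first-step thresholds; the procedure is step-up, so later thresholds are looser when several signals are real. Finally, keeping false-discovery control for AE screening, or purely descriptive reporting, is defensible in Phase 1. The SAP, however, chooses to test, and does not say within what family.

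**Conclusion.** The point holds as a low-cost improvement to the SAP, limited to formal comparison of Grade 1-2 AEs, local reactions and events from day 15 to day 50. No dose-ordered analysis is pre-specified, and safety is left under a correction of undefined scope.

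At 0.05, an exact trend test would raise power by 11 to 52 percentage points over the unordered exact test (13 - 2 = 11 at the mildest gradient, 81 - 29 = 52 at the steepest). Under BY with 5 to 10 tests and one real signal, the unordered test has at most about 6%.

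These sizes rest on assumed gradients, an assumed family, all seven cohorts filled with exactly 3, and the exact test standing for the listed unordered tests. Cohort size is the main constraint, so no choice of test makes moderate gradients reliably detectable.

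**What to change.** In SAP 8.2 and 8.5:

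- State that BY does not apply to AE and local-tolerability comparisons, and define the family to which it does apply.
- For each AE category, count volunteers with at least one event. Across the seven subcutaneous Stage I cohorts use one pre-specified exact dose-trend test (Cochran-Armitage), or the Cochran-Mantel-Haenszel correlation form, with the dose scores written down. Report it unadjusted and label it signal detection.
- Give exact 95% limits for each cohort and for the seven cohorts pooled.
- State that a non-significant result is not evidence that toxicity is unrelated to dose.

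The cost is SAP wording and a few lines of code, using data already collected. The downside is more false safety flags: in 10 independent tests at 0.05 the chance of at least one is at most 1 - 0.95^10 = 40%, and lower in practice because exact tests on so few volunteers are conservative.
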